7.3.1 Reporting Procedures

In the occurrence of an AE or SAE, during an IPPI, the implementation team will be instructed to complete the column in the provided binder on the final column of the resident preferences worksheet, providing a description of the event, the timing of the event, and the anticipated clinical response. If warranted, the team will be instructed to complete the IMPACT Serious Adverse Event (SAE) Report Form.

If an AE or SAE becomes apparent during a monthly call, the PI will request a completion of an Adverse Events or IMPACT Serious Adverse Event (SAE) Report Form, as applicable.

In the case of death, the site champion will also be instructed to call the PI to relay this information.

Following typical clinical safety protocols of the specific NH, a determination of continuation in the IPPI program will be determined by the NH clinical implementation team based on severity of event and relationship to the study. The decision for care alteration or necessary withdrawal from the study will be communicated with the PI through the Adverse Events form and/or if necessary, the second to last column of the Resident Preferences Worksheet. That column asks if the resident completed the IPPI program and if no, why not. For reporting, the decision of relatedness, expectedness, and severity of events will be defined as follows:

Severity of Event

All AEs will be assessed by a qualified medical professional on the NH implementation team using a protocol defined grading system to describe severity.

- Mild – Awareness of signs or symptoms, but easily tolerated and are of minor irritant type causing no loss of time from normal activities. Symptoms do not require therapy or a medical evaluation; signs and symptoms are transient.
- Moderate – Events introduce a low level of inconvenience or concern to the participant and may interfere with daily activities but are usually improved by simple therapeutic measures; moderate experiences may cause some interference with functioning.
- Severe – Events interrupt a participant’s usual daily activity and may require systemic treatment. Severe events are usually potentially life-threatening or incapacitating. Of note, the term “severe” does not necessarily equate to “serious”.

Expectedness

- Unexpected - Nature or severity of the event is not consistent with information about the condition under study or intervention in the protocol, consent form, product brochure, or investigator brochure.
- Expected - Event is known to be associated with the intervention or condition under study.

Relationship To Study Intervention

In the case of an AE, a qualified clinical professional on the implementation team at the resident’s NH will help judge the relationship of the AE to the study intervention. In light of the medical status of the resident participating in the study, the qualified clinical professional, will evaluate the degree to which the event was related to underlying disease/concurrent illness or study-related procedures, accidents, and other external factors. The clinician will indicate “Yes” in the final column of the Resident Preferences Worksheet and complete the Serious Adverse Event Report Form Template:

- Definitely Related – There is clear evidence to suggest a causal relationship, and other possible contributing factors can be ruled out. The clinical event occurs in a plausible time relationship to the IPPI intervention, follows a known or expected response pattern to the suspected intervention, that is confirmed by improvement on stopping and reappearance of the event on repeated exposure, and that could not be reasonably explained by the known characteristics of the subject’s clinical state. Depending upon severity of AE, the clinician may judge the event to warrant withdrawal from the study.

- Possibly Related – There is some evidence to suggest a causal relationship (e.g., the event occurred within a reasonable time after an IPPI happened or follows a known or expected response pattern to the suspected intervention). However, other factors may have contributed to the event (e.g., the participant’s clinical condition, other concomitant events). An AE rated as “possibly related” soon after discovery, can be flagged as requiring more information and later be upgraded to definitely related”, as appropriate.
- Not Related – The AE is clearly not related and completely independent of study intervention administration, and/or evidence exists that the event is definitely related to another etiology. For example, another cause of the event is most plausible and/or a clinically plausible temporal sequence is inconsistent with the onset of the event and the study intervention and/or a causal relationship is considered biologically implausible

All adverse events that are serious (SAE) and unexpected (i.e., have not been previously reported for the study’s intervention) will be reported to the IMPACT Collaboratory Regulatory and Data Team Leader ([name]), NIA IMPACT Collaboratory PO ([name]), and the IMPACT Collaboratory Safety Officer within 48 hours of the study’s knowledge of SAE.

- Only those adverse events that are serious (SAE), unexpected, and related to the intervention must also be reported to Advarra IRB. Unexpected and unrelated SAEs will be reported to Advarra IRB on a case-by-case basis if requested by the IMPACT Collaboratory Safety Officer or NIA IMPACT Collaboratory PO.

All deaths will be reported to IMPACT Collaboratory Regulatory and Data Team Leader ([name]), NIA IMPACT Collaboratory PO ([name]), and the IMPACT Collaboratory Safety Officer within 24 hours of study’s knowledge of death.

- Advarra IRB does not require the specific reporting of death outside of the SAE reporting requirement above, but they will be notified on a case-by-case basis if requested by the IMPACT Collaboratory Safety Officer or NIA IMPACT Collaboratory PO.

All unanticipated problems (UPs) will be reported to the IMPACT Collaboratory Regulatory and Data Team Leader ([name]), Advarra IRB, NIA IMPACT Collaboratory PO ([name]), and the IMPACT Collaboratory Safety Officer within 48 hours of the study’s knowledge of the event.

The summaries of all previously reported unexpected and related SAEs, deaths, and UPs, as well as all other SAEs and AEs will be reported to IMPACT Collaboratory Regulatory and Data Team Lead ([name]), Advarra IRB, NIA IMPACT Collaboratory PO ([name]), and the IMPACT Collaboratory DSMB Chair (or the project’s Safety Officer) at a minimum every 6 months, or at a frequency requested by the IMPACT Collaboratory Safety Officer or NIA IMPACT Collaboratory PO.

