However, a person could become agitated during an IPPI if it is not explained well by a care partner, as with routine care. In these instances, behaviors such as wandering or becoming aggressive could occur at the same rate with which they occur during typical clinical care. Further, the population served by this intervention is by definition a vulnerable medical population experiencing dementia and often multiple other chronic illnesses. We would expect that due to the age and illness severity of the PLWD that the occurrence of falls, emergency room/hospitalizations, and death can reasonably be expected. Implementation team care partners are already trained by their specific facility in managing safety concerns and health events that may occur during typical care and they will behave the same during enrollment in the IPPI program. The care partners would act according to their facility's rules and expectations.

In the case of an adverse event occurring during study participation, an Adverse Event

form would be submitted to the PI within 3-days of the event (see procedural expectations below in 7.3). In the case of death of a resident, the site champion will be advised to call the PI to notify her of the passing.

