7.3.2 Follow-up for Adverse Events

NH implementation teams will follow all existing health and safety protocols in their NHs for procedures following a safety-related or health-related event until the AE or SAE is resolved or the person is considered stable.

Upon resolution of the event, the site champion will provide additional information to the PI to indicate the timing of resolution/stabilization of the event. All AEs occurring while in the study will be documented appropriately regardless of relationship to the intervention. All AEs will be followed to adequate resolution.

Any medical condition that is present at the time that the participant is screened will be considered as baseline and not reported as an AE. However, if the study participant's condition significantly deteriorates at any time during the study, it will be recorded as an AE.

The site champions will record all reportable events with start dates occurring any time after participant enrollment for 7 (for non-serious AEs) or 30 days (for SAEs) after the last day of study participation.

During each monthly check-in the PI will inquire about the occurrence of AE/SAEs since the last call. Events will be followed for outcome information until resolution or stabilization.

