16 SUPPLEMENTS/APPENDICES

While any member of the implementation team can complete these forms, we anticipate the champion(s) being primarily responsible. We will ask that the champion(s) submit data to the research team in batches with the 3 month and 6 month electronic data. These forms can be scanned and emailed or faxed to the project manager, [name] via encrypted email at [contact] or private fax at [contact].

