***email address will be used to identify if individual completed the Emotion Focused Communication Training**

IPPI Program – Resident Preferences Worksheet

Site champion(s) will maintain a password protected list of the name of each resident that is enrolled into the IPPI program along with a unique ID# that is determined by the champion(s). This password protected file will be shared with the PI who will then link the data from this worksheet to the electronic medical record data prior to deidentifying.

After completing a resident's preference assessment, identify and record their most important preferences in the column "Important Preferences." Next, review the list of IPPI protocols then record the protocols that match the resident's important preferences in the "Matching IPPIs" column. Review the list of matching IPPIs with the implementation team member(s) that will be facilitating the activity with the resident and let them chose which IPPI activities (1-2) they are most comfortable doing. After they've chosen the IPPI activities, record their selection in the "IPPIs Selected" column. Identify one or more resident behaviors that are the target outcome for the intervention as indicated on the MDS Section E. Finally, note if the resident completed the project and if there were any adverse events.

Resident Unique ID#	Important Preferences	Matching IPPIs	IPPIs Selected by implementation team	Supplies Needed Location	Which targeted behavior(s) do you hope the IPPI will remediate? Check all that apply	Did the resident complete the IPPI Project? Yes No If no, why did the individual not complete the project?	Did the resident have any adverse events? Yes No If Yes, complete Serious Adverse Event Report Form
	•	•	•	○	 Physical behavioral symptom  Verbal behavioral symptom  Other behavioral symptom  Rejection of Care  Wandering  Depressive Mood Symptoms	○	○

Observation Checklist of Fidelity to IPPI Protocol conducted by Champion

Did the person delivering the IPPI do any of the following?

1. Yes No N/A Introduce self to resident
2. Yes No N/A Introduce IPPI activity to resident
3. Yes No N/A Consider possible distractions (background noise, visual/tactile)
4. Yes No N/A Check that individual could hear or was wearing hearing aids if applicable
5. Yes No N/A Interrupt resident in the middle of a visit (reverse coded)

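### Section 7.3.1 and the Appendix A worksheet conflict with the protocol's own rules on which adverse events are recorded, how soon they are sent, and on which form

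*Combined protocol and SAP*

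**What the plan says.** Section 7.3.1 opens with the instruction to staff: "In the occurrence of an AE or SAE, during an IPPI, the implementation team will be instructed to complete the column". The column is the final one of the Resident Preferences Worksheet. The serious-event form follows where warranted. For events that surface on a monthly call, the PI asks for whichever of the two forms applies. The same section requires a qualified professional on the site team to grade every AE as mild, moderate or severe. Its text on relatedness, which concerns AEs in general, has the clinician mark Yes in the worksheet column "and complete the Serious Adverse Event Report Form Template".

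Other places bear on the same events:

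- Section 7, opening text, covers participation as a whole ("In the case of an adverse event occurring during study participation, an Adverse Event") and sets the deadline: "form would be submitted to the PI within 3-days of the event". It refers to 7.3 for procedure.
- Section 7.3 defines an AE by its timing relative to involvement in the research, related or not.
- Section 7.3.2 states: "All AEs occurring while in the study will be documented appropriately regardless of relationship to the intervention". It adds: "The site champions will record all reportable events with start dates occurring any time after participant enrollment for 7" days (non-serious) or 30 days (serious) after the last day of participation.
- Section 6.2.3 has AEs go directly to the PI, following 7.3.
- Section 6.2.2 has the PI collect the worksheet every three months. Section 16 asks champions to "submit data to the research team in batches with the 3 month and 6 month electronic data".
- The last column of the Appendix A worksheet asks: "Did the resident have any adverse events? Yes No If Yes, complete", and then names the Serious Adverse Event Report Form.

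**The concern.** The section that sites will consult for reporting is 7.3.1, and the paper in their hands is the worksheet. Section 10.3.1 says that implementation staff receive no human-subjects training, so the wording of the instruction and the form carries the process. A site that follows both literally would leave an event between sessions out of the column. It could let a noted event wait for the next batch, and it would put a non-serious event on the serious-event form.

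This matters for three reasons. The 24-hour (deaths) and 48-hour (unexpected serious events) onward reports in 7.3.1 run from the study's knowledge, so a late site report delays them without any breach being visible. The safety review in 9.3 depends on someone noticing repeated events. The periodic summaries in 7.3.1 separate serious from other events, and that split is only as good as the form used. The residents are a vulnerable group enrolled under a waiver of consent.

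**Working it through.** No sample size, power or event count is involved, so the check sets the texts side by side.

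| Question | 7.3.1 instruction, worksheet and batch rule | Rule stated elsewhere |
|---|---|---|
| Which events? | Those in a session (7.3.1) | All during participation (section 7, 7.3, 7.3.2), then 7 or 30 days more (7.3.2) |
| How soon? | Worksheet collected every three months (6.2.2); binder forms batched at 3 and 6 months (16) | 3 days from the event (section 7) |
| Which form? | Serious-event form for any AE (worksheet; relatedness text of 7.3.1) | Serious-event form only if warranted or applicable (7.3.1, opening paragraphs); separate AE form (sections 3, 6.1, 7, 7.3.1) |
| Severity? | No field on the worksheet or on the serious-event form | Grade for every AE (7.3.1) |

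1. **Scope.** Two of the protocol's own provisions cannot work under the in-session trigger. The 7- and 30-day windows fall after the last day of participation, when no sessions take place. Section 7.3.1 also counts an event as possibly related if it happens within a reasonable time after a session, yet the recording trigger leaves such an event out.

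2. **Timing.** Sections 6.2.3 and 7 both send the reader to 7.3, but 7.3 to 7.3.2 do not repeat the 3-day deadline for sites. Section 16 introduces the appended forms and exempts none of them. A reader of 7.3.1, Appendix A and section 16 alone would therefore see a three-month cycle and no 3-day rule.

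3. **Form.** The serious-event form has 15 numbered items. Item 8 (category) offers six options, all of them kinds of serious event. A non-serious event has no correct answer there.

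4. **Severity.** The same form records expectedness (item 4) and relatedness (item 11) but not mild, moderate or severe. The worksheet has none of the three.

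5. **The AE form.** Section 3 says the binder will hold forms for adverse events. The binder list in 10.2 names only the training record, the worksheet and the checklist, and the Appendix A text available for review shows no AE form. Its content, including any severity field, cannot be judged from this text.

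**The case against.** The strongest reply is that 7.3.1 does not stand alone. Section 7 requires a form within 3 days for any event during participation. Section 6.2.3 has events go directly to the PI. Section 7.3.2 tells champions to record events from enrolment onward. Monthly calls ask about events, and deaths are phoned to the PI. A specific safety rule would normally be read as overriding a general batch rule, and the three-monthly worksheet collection in 6.2.2 is there to check preference matching.

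Much of this stands, and it rules out several stronger readings that a reader might infer:

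- *That events between sessions reach the study only through recall on a monthly call.* Sections 6.2.3, 7 and 7.3.2 are also operating instructions, and none is limited to sessions.
- *That nearly all events go unrecorded.* Two 10-minute sessions are 20 of 7 × 24 × 60 = 10,080 minutes, about 0.2% of a week. That is a share of clock time, not of events, and it would matter only if the other routes did not exist.
- *That reports will arrive three months late.* That would need the 3-day form and successive monthly calls all to fail.
- *That non-serious events are lost.* Section 7.3.1 provides for an AE form, and its periodic summaries include all other AEs.
- *That one rule requires a graded report within 3 days.* The deadline and the grading are separate rules. The severity point is a missing field, not a direct contradiction.

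What the reply does not remove is the conflict itself. The direct route in 6.2.3 leads back to 7.3. A monthly call cannot secure 3 days. Its scripted question in 7.3 asks about unexpected changes, while the same section says that falls, hospital visits and deaths can be expected, so staff may not mention falls or hospital visits.

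**Conclusion.** The point holds as an internal inconsistency, wrong as written. On scope, timing and form, the 7.3.1 wording, the worksheet and the batch rule say something different from rules that the protocol states elsewhere. On severity, the forms shown have nowhere to record a required grade.

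The likely consequence is capture that differs between sites, some late reports, and some non-serious events filed as serious. Certain loss of events is not supported, because the other routes exist. The documents give no adverse-event rate, so the number of events affected cannot be estimated. The only figures available are the stated intervals: 3 days under section 7, monthly for the calls, and three months for the batches.

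The conclusion assumes that sites act on the 7.3.1 text and the worksheet as worded. It also rests on the Appendix A text as supplied; an AE form with a severity field, if one exists, would meet part of the last point. No efficacy or feasibility analysis is affected.

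**What to change.** Reconcile the passages to the rules already stated:

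1. In 7.3.1, delete the in-session limit so that the instruction covers any AE or SAE during participation and within the 7- and 30-day windows of 7.3.2.
2. In 7.3.1 and section 16, state that AE and SAE forms follow the existing 3-day rule of section 7 and are exempt from the 3- and 6-month batches.
3. In the worksheet's last column and the relatedness text of 7.3.1, send non-serious events to the AE form and only serious events to the serious-event form.
4. Provide a mild/moderate/severe field on the forms used, and list the AE form in 10.2 and Appendix A.

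The cost is a wording amendment and small form edits. Sites will file somewhat more reports of expected events, but 7.3.2 already asks for these. The design, sample size and clinical rules do not change.

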7.3.2 Follow-up for Adverse Events

NH implementation teams will follow all existing health and safety protocols in their NHs for procedures following a safety-related or health-related event until the AE or SAE is resolved or the person is considered stable.

Upon resolution of the event, the site champion will provide additional information to the PI to indicate the timing of resolution/stabilization of the event. All AEs occurring while in the study will be documented appropriately regardless of relationship to the intervention. All AEs will be followed to adequate resolution.

Any medical condition that is present at the time that the participant is screened will be considered as baseline and not reported as an AE. However, if the study participant's condition significantly deteriorates at any time during the study, it will be recorded as an AE.

The site champions will record all reportable events with start dates occurring any time after participant enrollment for 7 (for non-serious AEs) or 30 days (for SAEs) after the last day of study participation.

During each monthly check-in the PI will inquire about the occurrence of AE/SAEs since the last call. Events will be followed for outcome information until resolution or stabilization.

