6 STUDY PROCEDURES

The Schedule of Evaluations in section 6.1 includes all study evaluations.

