6.1 Schedule of Evaluations

Assessment	Pre-enrollment	Baseline, Enrollment (Day 0)	Each IPPI (2x a week for 180 days)	3-month Assessment (~Day 90)	6-month Assessment (~Day 180)	Post Intervention Trial
Organizational Readiness for Implementing Change (ORIC)	X					
MDS 3.0 data of residents BIMS scores and Section D and E Responses (rolling ; each resident assessed for enrollment to serve as baseline assessment, 3-mon, and 6-mon)	X	X		X	X	
Identify Implementation team (Y/N)	X					
Virtual Coaching session attendance (Y/N)	X			X	X	
Emotion-Focused Communication Training (EFCT) completion (Y/N)	X					
Emotion-Focused Communication Training (EFCT) pre and post-test (knowledge, efficacy)	X					
IPPI Training (watching 2 videos) completed (Y/N)	X					
Resident Preferences Worksheet (rolling)		X	X	X	X	
Care Plan Documentation (Y/N)		X	X	X	X	

Fidelity Assessment with Pragmatic Checklist (observation of 1st IPPI between each resident and implementation team member delivering IPPI)			X (1 st IPPI only)			
Exit Interview (communication, acceptability, feasibility, appropriateness, facilitators, and barriers)						X
Troubleshooting (count of contacts)	X	X	X	X	X	
Intervention Withdrawal form			X			
Adverse Events form			X			

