7.3 Adverse Events and Serious Adverse Events

Adverse and serious adverse events for this study are defined as follows:

Adverse Event (AE): Any unfavorable medical or behavioral outcome in a clinical research study participant, including but not limited to expression of extreme distress (defined as a person specific change in behavior that is uncharacteristic of the individual

whereby the individual is visibly upset and/or inconsolable), an illness event (i.e., a heart attack, stroke), or a fall temporally associated with the participants' involvement in the research, whether or not considered related to participation in the research.

Serious Adverse Event (SAE): Any adverse event that:

- Results in death
- Is life threatening, or places the participant at immediate risk of death from the event as it occurred
- Requires or prolongs hospitalization
- Causes persistent or significant disability or incapacity
- Is another condition which investigators judge to represent significant hazards

Unanticipated Problem (UP) Definition: Any incident, experience, or outcome that meets all of the following criteria:

- Unexpected, in terms of nature, severity, or frequency, given (a) the research procedures that are described in the protocol-related documents, such as the IRB-approved research protocol and informed consent document; and (b) the characteristics of the study population;
- Related or possibly related to participation in the research;
- Suggests that the research places participants or others at a greater risk of harm (including physical, psychological, economic, or social harm) than was previously known or recognized.

Adverse events are not anticipated to occur in response to the intervention beyond the routine experience of events in clinical care. We expect no SAEs to occur as a result of an IPPI activity because they are meant to be short, enjoyable activities. We would expect that due to the age and illness severity of the people living with dementia that the possibility of falls, emergency room/hospitalizations, and death can reasonably be expected. During our monthly check-in calls with the implementation team, we will ask if any adverse events have occurred, *“Have there been any unexpected changes in resident behaviors or health while participating in the study?”*

NHs will otherwise follow their regulated health and safety protocols and responses.

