8 INTERVENTION DISCONTINUATION

Participating in the IPPI intervention is optional for residents. Residents can refuse participation at any time. The staff can choose to discontinue the IPPI with any participant based upon their clinical judgement and the individual may be withdrawn from the study.

Withdrawal can also follow a significant health change or hospitalization that makes the participant unable to continue to participate in the IPPI intervention activities. Implementation team clinical staff will make a judgement call.

Participants may also be withdrawn due to death. Residents living with dementia in a NH are a vulnerable population, health events are common and anticipated (i.e. falls).

Participants may also be withdrawn from the study if the individual leaves the NH to move to another NH. The resident must continue to reside in the same NH for the 6-months of the study period to be engaged in the intervention.

For all reasons of withdrawal, the implementation team for a given resident will communicate the withdrawal to the PI with the second to last column on the Resident Preferences Worksheet stating the date and the reason.

While there is no formal plan for replacement of subjects, due the rolling nature of enrollment, additional eligible residents may be added to the study to accommodate a withdrawal if it occurs within the first 3 consecutive months of the study.

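### The 7- and 30-day adverse event windows after last participation are not carried into the scripted question, form triggers, schedule, withdrawal record or transfer provision, so late events may be missed

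*Combined protocol and SAP*

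**What the plan says.** Section 7.3.2 gives champions the duty to record reportable events starting "any time after participant enrollment for 7 (for non-serious AEs) or 30 days (for SAEs) after the last day of study participation". It also has the PI ask at each monthly check-in about events since the previous call, without limiting this to residents still taking part.

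Other places are narrower:

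- Section 6 states: "The Schedule of Evaluations in section 6.1 includes all study evaluations". In 6.1 the Adverse Events form and the Intervention Withdrawal form are marked only under the column "Each IPPI (2x a week for 180 days"). The last column, for the period after the intervention, holds only the staff exit interview.
- Section 7.3 scripts the monthly question as "Have there been any unexpected changes in resident behaviors or health while participating in the study".
- Section 7 asks for an Adverse Event form within 3 days for events that occur while the resident takes part. The first reporting instruction in 7.3.1 is limited to events in an IPPI session.
- Section 8 has withdrawals communicated to the PI "with the second to last column on the Resident Preferences Worksheet stating the date and the reason". That column in the Appendix A worksheet offers yes or no and then asks "If no, why did the individual not complete the project". It has no prompt for a date. Sections 6.1 and 6.2.3 name a separate Intervention Withdrawal form, which 6.2.3 says carries the date, but section 8 does not use it.
- Section 8 also states: "Participants may also be withdrawn from the study if the individual leaves the NH to move to another NH". Nothing says how later events in such a resident would become known.

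**The concern.** The 7- and 30-day windows start on a resident's last day of participation. To observe them, the study needs that date, a prompt that reaches past it, and someone who can still see the resident. Each of these is weak or absent somewhere in the protocol.

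The period matters because section 8 allows withdrawal after a significant health change or hospitalization, so further serious events soon afterwards are plausible. The expedited reporting times in 7.3.1 (24 hours for deaths, 48 hours for unexpected SAEs) run from when the study learns of the event. An event that nobody detects starts no clock, and it is also absent from the summaries that go at least every 6 months to the IRB and the safety oversight roles. Those summaries could then be read as more complete than they are.

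**Working it through.** The plan gives no event rate or other figure to reproduce here. The check is a comparison of the texts, followed by timeline arithmetic.

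**1. Does each route reach past the last day of participation?**

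| Place | Coverage | Reaches the 7/30-day window? |
|---|---|---|
| 7.3.2, champions' duty | Whole window | Yes |
| 7.3.2, PI's monthly inquiry | Events since the previous call | Yes, while calls continue |
| 7.3.1, events found on a call | PI requests a form | Yes, if the call reveals the event |
| 7.3, scripted question | Changes while taking part | No |
| 7, form within 3 days | Events while taking part | No |
| 7.3.1, worksheet entry | Events in a session | No |
| 6.1, Adverse Events form | Per-session column, 180 days | No |
| 8 and Appendix A worksheet | Withdrawal and reason; no date prompt | Start of window not reliably recorded |
| 8, move to another home | No route stated | No |
| 10.3.1, monthly calls | Throughout the grant period; no end date given | Cannot be determined |

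**2. Unscheduled time for a completer.** The window ends at day 180 + 7 = 187 for non-serious events and at day 180 + 30 = 210 for SAEs. The schedule's column ends at about day 180, so 7 and 30 days are unscheduled.

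**3. Completers whose window could outlast the calls.**

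Inputs: rolling enrollment over 3 to 4 months (section 2.2), taken as E = 90 or 120 days; 180 days of sessions (6.1); 105 to 110 residents (Précis, Sample Size and Population).

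Assumptions, not in the documents: entry is uniform over the enrollment period, every resident completes, and calls stop when the last resident reaches day 180.

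A resident who enters on day e has a window of w days ending at e + 180 + w. The last call is at E + 180. The window runs past it when e > E − w, so the share is w/E.

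- SAEs, 4-month enrollment: 30/120 = 25%, or 105 × 0.25 = 26.25 to 110 × 0.25 = 27.5 residents (about 26 to 28).
- SAEs, 3-month enrollment: 30/90 = 33.3%, or 105/3 = 35 to 110/3 = 36.7 residents (about 35 to 37).
- Non-serious events: 7/120 = 5.8% to 7/90 = 7.8%.

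The part of the SAE window falling after the last call, averaged over all completers, is w²/(2E): 900/240 = 3.75 days or 900/180 = 5.0 days of the 30, that is 12.5% or 16.7%.

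If calls run 30 days longer, both shares are 0%. With 4-month enrollment the last resident finishes at about month 4 + 6 = 10 and the last SAE window closes at about month 11.

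**The case against.** The strongest reply is that the window is already assigned. Section 7.3.2 makes champions responsible for it and adds a monthly inquiry that is not limited to participation. Section 7.3.1 turns an event found on a call into a form, and section 10.3.1 runs calls through the grant period. Sections 7 and 7.3.1 have deaths telephoned to the PI. Completers, and withdrawn residents who stay in the home, remain visible to staff. Event-triggered forms marked in one schedule column do not cancel an explicit duty elsewhere. Most of this stands, and it limits the point to events that may be missed.

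A reader might go further in four ways that the documents do not support:

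- **That every collection route stops at participation and serious events will be lost.** The duty and inquiry in 7.3.2 contradict this.
- **That the unscheduled days measure lost events.** Thirty of a completer's 210 days (14%) are unscheduled, but they are not unobserved while champions record and calls continue.
- **That batching defeats the window.** Section 16 asks champions to "submit data to the research team in batches with the 3 month and 6 month electronic data", but the champion, not the PI, observes the window. On-site staff know of a withdrawal when it happens. Section 7 also sets a 3-day route for adverse event forms.
- **That the Intervention Withdrawal form does not exist because Appendix A does not show it.** Section 3 says the binder holds forms for adverse events and withdrawals, and the appendices available for review may be incomplete. The firmer point is that section 8 relies on a worksheet column without a date prompt.

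The reply leaves three gaps open: nothing puts departed residents on the call agenda, no text covers events after a transfer, and no end date for the calls is tied to the last 30-day window.

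**Conclusion.** The inconsistency is real but moderate. Section 7.3.2 sets 7- and 30-day windows that the scripted question, the form triggers, the schedule and the withdrawal record do not carry through. Events after withdrawal or completion may be missed. The risk is clearest for residents who move to another home, where no text offers a route; their number cannot be estimated from the documents.

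For completers, the 25% to 33% is the share whose SAE window would outlast the calls. It rests on the assumed stopping date for calls, uniform entry and full completion; it is not a share of events lost. Even on that assumption, calls span the full SAE window for about 67% to 75% of completers, and the champions' own duty applies to all.

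Resident and staff outcome analyses are unaffected. The consequence is for the completeness of the SAE and death summaries. The documents plan no formal risk estimate for the later trial, so none is claimed to be biased.

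**What to change.** Reconcile sections 6.1, 7, 7.3, 7.3.1 and 8 and the Appendix A worksheet with the window in 7.3.2:

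1. Reword the scripted question in 7.3 and the form triggers in 7 and 7.3.1 so that they cover the full 7- and 30-day windows. On each call, name recently departed residents by study ID.
2. Add the post-participation window to the schedule in 6.1.
3. Make the date mandatory on the withdrawal record, have section 8 and 6.2.3 use the same record, and send it to the PI when the withdrawal happens.
4. State that monthly calls run until 30 days after the last resident's last day.
5. Reconcile the 30-day window with the transfer provision in section 8, and report how many residents had a window that was not fully observed.

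The cost is wording changes to the schedule, script and forms, and about one more month of the existing calls at the last homes to finish.
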